10.2 Sample Size and Accrual

This is a Phase II study in which the primary aim will be to determine the complete response rate to up front pembrolizumab. The treatment paradigm of this trial will be considered worthy of further evaluation if at least 40% of patients achieve CR at PET#2 (defined as Deauville 1-3).

The target sample size for the primary response analysis is 26 patients, with 4 additional patients to be accrued to account for dropout, so that the total target sample size is 30 patients in order to increase the CR rate to single agent pembrolizumab from the baseline level of 20% in relapsed/refractory patients, to 40% with a power of 84% at an alpha level of 10%. For the analysis of complete response by PET, a single arm single stage Bayesian design with 26 patients may also be used. Response is defined as a Deauville score of 1-3 after the initial treatment with pembrolizumab alone. The posterior probability of a response rate being greater than 50% will be calculated using a non-informative prior

distribution. With 26 patients, the following table gives this posterior probability for an observed number of responses.

Observed number of responses/26: 11 12 13 14 15 Probability that response rate > 40%: 0.61 0.75 0.86 0.92 0.96

Therefore, to be more than 80% sure that the response rate exceeds 40%, at least 13 of 26 responses would need to be observed in the total population. After PET#3, patients will be analyzed as a total population as well as by age cohort for response rate, PFS, and OS.

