consolidation treatment with pembrolizumab for 2 years total (3 doses in induction + 32 doses in consolidation). Those with

	Deauville 1, 2, 3 (PET#3) will continue to follow-up if they receive all 6 AVD doses successfully. If they were unable to receive the full intended 6 cycles of chemotherapy for stage III/IV disease because of poor tolerance, they should receive consolidation with pembrolizumab for up to 1 year (3 doses in initiation + 14 doses in consolidation).
	Total Study Duration: 9 weeks of initiation therapy with pembrolizumab + 16-24 weeks of chemotherapy + consolidation for up to 96 weeks (select elderly patients) + 2 years of follow-up
Statistical Methodology	The treatment paradigm of this trial will be considered worthy of further evaluation if at least 40% of patients achieve CR at PET#2 (defined as Deauville 1-3). In order to have 84% power to detect an increase from the historical control of 20% rates of CR for patients with rel/ref cHL treated with pembrolizumab, at a one-tailed alpha of 10%, approximately 26 evaluable patients will be required total. The accrual goal is 30 patients to account for possible unevaluable patients.

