10.3 Data Analyses Plans

10.3.1 Analytic Plan for Primary Objective

To assess the primary objective of response rate following PET (2) performed after 3 doses of pembrolizumab, we will assess PET response using the 5 point Deauville criteria. Patients with a Deauville score of 1-3 will be considered a complete response. Patients will be evaluable for response assessment if they have received at least one dose of pembrolizumab. Response will be determined in all patients after induction (PET # 2) and after chemotherapy (PET # 3) using a proportion and an exact binomial 95% confidence interval. It will be observed whether 50% is in the confidence interval. Continuous futility monitoring will occur using the method of Lee & Liu. ⁵⁰ While this method may be used to identify a futile level of response after each patient, it will begin monitoring after 10 patients. Futility will be indicated if at most 1/10, 3/15 or 5/20 evaluable patients have a response, assuming 26 total evaluable patients will be observed. For these calculations, futility means that the posterior probability that the response rate exceeds 50% is less than 10%.

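### At n = 26 no cut-off gives 84% power within one-sided alpha 10%, and the written go criterion, read as an observed 40% (11/26), has 47.9% power at a true 40%

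*Combined protocol and SAP*

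**What the plan says.** The Study Summary (Statistical Methodology) gives the design basis: "In order to have 84% power to detect an increase from the historical control of 20% rates of CR", and "at a one-tailed alpha of 10%, approximately 26 evaluable patients will be required total". Section 10.2 repeats it, with 20% taken from relapsed/refractory patients and the CR rate to rise "to 40% with a power of 84% at an alpha level of 10" percent. The target is 26 evaluable patients, "with 4 additional patients to be accrued to account for dropout", for a total of 30.

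Four statements bear on how the result will be judged:

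- Section 10.2, also in the Summary: "The treatment paradigm of this trial will be considered worthy of further evaluation if at least 40% of patients achieve CR at PET#2".
- Section 10.2, as an option: "a single arm single stage Bayesian design with 26 patients may also be used".
- Section 10.2, for that option: "to be more than 80% sure that the response rate exceeds 40%, at least 13 of 26 responses would need to be observed".
- Section 10.3.1, for the CR proportion and its exact 95% interval: "It will be observed whether 50% is in the confidence interval". No consequence is attached to the answer.

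No test of 20% against 40% is named, and no critical number of responses is given for one.

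**The concern.** A power figure belongs to a rule. With 26 patients and a binary endpoint the rule must be a whole number of responses, so the stated pair (alpha 10%, power 84%) can be compared with every rule available. If none matches, the stated power of the primary endpoint is not a property of the trial.

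The written go criterion raises a second problem. It puts the threshold at the same 40% that serves as the design alternative. A threshold on the observed rate placed at the true rate is passed only about half the time, which cannot be squared with 84%.

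The go/no-go decision is at stake. With 9 or 10 CRs among 26, an exact one-sided test rejects 20% (p = 0.059 and 0.023), yet the observed rates of 34.6% and 38.5% miss the written 40%. The same data could be called positive or negative afterwards. At a true 40% this happens with probability 0.7745 − 0.4787 = 0.296, about three times in ten.

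**Working it through.** **Inputs.** From 10.2 and the Summary: null rate p0 = 0.20, alternative p1 = 0.40, one-sided alpha 0.10, n = 26 evaluable, up to 30 enrolled. The hypothesised CR rate of 50% is in 2.1.

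**Reproducing the 84%.**

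- Normal approximation: Φ{[(p1 − p0)√n − z₀.₉₀√(p0(1 − p0))] / √(p1(1 − p1))} = Φ{[0.2 × 5.099 − 1.2816 × 0.4] / 0.4899} = Φ(1.035) = 85.0%.
- Arcsine approximation: Φ{(2 arcsin√0.4 − 2 arcsin√0.2)√n − z₀.₉₀} = Φ{0.4421 × 5.099 − 1.2816} = Φ(0.973) = 83.5%.

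The stated 84% lies between them, so it looks like an approximation rather than a slip.

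**Exact rules at n = 26.** With X ~ Binomial(26, p), the rule is go if X ≥ r:

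| r | observed rate | P(X ≥ r), p = 0.20 (alpha) | p = 0.40 | p = 0.50 |
|---|---|---|---|---|
| 8 | 30.8% | 0.1313 | 0.8784 | 0.9855 |
| 9 | 34.6% | 0.0592 | 0.7745 | 0.9622 |
| 10 | 38.5% | 0.0232 | 0.6358 | 0.9157 |
| 11 | 42.3% | 0.0079 | 0.4787 | 0.8365 |
| 13 | 50.0% | 0.0006 | 0.1993 | 0.5775 |

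The cut-off of 8 exceeds alpha 10%. The cut-off of 9 is the lowest that respects it, so 77.4% is the best power at a valid whole-number cut-off.

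**Ceiling.** A randomised test of size exactly 10% is the most powerful possible. It rejects at X ≥ 9, and at X = 8 with probability (0.10 − 0.0592)/(0.1313 − 0.0592) = 0.566. Its power is 0.7745 + 0.566 × (0.8784 − 0.7745) = 0.833, still below 84%.

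**Written criterion.** 0.40 × 26 = 10.4, so an observed 40% needs 11 responses: alpha 0.8%, power 47.9% at 40%, failure probability 1 − 0.4787 = 52.1%. The stated power implies 1 − 0.84 = 16%.

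**Other evaluable numbers.**

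| n | reject 20% at alpha ≤ 10%: r, alpha, power at 40% | observed ≥ 40%: r, alpha, power at 40% |
|---|---|---|
| 26 | 9, 0.059, 0.774 | 11, 0.008, 0.479 |
| 27 | 9, 0.074, 0.816 | 11, 0.011, 0.542 |
| 28 | 9, 0.090, 0.852 | 12, 0.005, 0.449 |
| 29 | 10, 0.049, 0.785 | 12, 0.007, 0.510 |
| 30 | 10, 0.061, 0.824 | 12, 0.009, 0.569 |

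Within this range only n = 28 meets both 84% and 10%.

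**Futility looks.** Applying only the three printed boundaries in 10.3.1 (at most 1/10, 3/15, 5/20) as binding stops, 8/26 has alpha 10.1% and power 81.1%, 9/26 has 5.3% and 74.1%, and 11/26 has 0.8% and 47.5%. They do not rescue the stated figure.

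Those boundaries also disagree with their own definition, a posterior probability below 10% that the rate exceeds 50%. Under a uniform prior (an assumption; it reproduces the 0.61, 0.75 and 0.86 tabulated in 10.2 for 11 to 13 responses), that definition allows stopping at up to 2/10 (0.033), 4/15 (0.038) and 7/20 (0.095). The printed values are instead the largest counts meeting a 40% threshold: 0.030, 0.065 and 0.096.

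**The case against.** The strongest reply is that 84% is a sound textbook approximation. The Summary says approximately 26, the exact requirement is only two patients more, and the randomised ceiling of 83.3% is 0.7 points below the stated figure. An uncorrected z-test (p = 0.085) or a mid-p test (0.095) would reject at 8/26 and have 87.8% power. On this view the mismatch is only binomial discreteness. All of that is correct, and if it were the whole matter the point would be small. But the 8/26 rule has a true type I error of 13.1%, so it does not deliver the stated 10%.

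Second, the 47.9% rests on reading the 40% as an observed proportion. In both places the criterion sits next to the power calculation, where 40% is the target rate. That reading is possible, but it leaves the plan with no critical value and a best valid power of 77.4%, so a correction is needed either way.

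Third, the protocol expects 50% CR, and at 50% the 11/26 rule has 83.7% power and the 9/26 rule 96.2%. This softens the practical consequence. The plan, however, ties its 84% to 40%.

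Fourth, this is a single-arm phase II trial whose estimate and interval stand under any rule. That is true, and it limits the defect to the stated power and the go/no-go decision.

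Finally, which rate the futility boundaries fit depends on the prior. That inconsistency is secondary, and the conclusion here does not need it.

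**Conclusion.** The concern holds. No whole-number cut-off at 26 evaluable patients gives 84% power at a true 40% while keeping exact one-sided alpha against 20% at or below 10%; the best valid rule, 9/26, gives 77.4%. The larger discrepancy is with the written criterion: as an observed proportion it has alpha 0.8% and power 47.9%, and over 26 to 30 evaluable patients its power at 40% runs from 44.9% to 56.9%. The optional 13/26 threshold has 19.9%. The results assume independent binomial responses and, apart from the futility calculation, no early stopping. The 47.9% also assumes the plain reading of the criterion. No approximation bridges 84% and 47.9%, so the stated power and the deciding cut-off must be corrected.

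**What to change.** In the Summary and 10.2, say whether 40% is an observed threshold or the target rate, and replace the 84%/10% statement with the exact properties of the rule that decides. There are three options:

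- **Keep the written 40% criterion.** State at least 11 of 26 evaluable patients with CR at PET#2, exact one-sided alpha 0.8% against 20%, power 47.9% at 40% and 83.7% at 50%. This costs wording only, with a less favourable stated power.
- **Decide by rejecting 20%.** State at least 9 of 26, alpha 5.9%, power 77.4% at 40%. This replaces the 40% criterion (9/26 is 34.6%) and needs an amendment that says so.
- **Hold 84% within 10%.** Use 28 evaluable patients and at least 9 CRs: alpha 9.0%, power 85.2%. This stays within 30 enrolled but leaves 2 rather than 4 patients for dropout, and it also replaces the 40% criterion by amendment.

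Give the cut-off for the evaluable number actually reached: for the 40% criterion, 11 at n = 26–27 and 12 at n = 28–30; for rejection of 20%, 9 at n = 26–28 and 10 at n = 29–30. Label the 13/26 threshold and the check on 50% as supportive. State whether futility is binding, and quote futility-adjusted power only after the boundaries and the definition in 10.3.1 have been reconciled.

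### Section 10.2 sets three unranked thresholds for the primary CR endpoint (about 9, 11 and 13 of 26), so the verdict is not determined for results of 9 to 12 of 26

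*Combined protocol and SAP*

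**What the plan says.** Three statements in section 10.2 (Sample Size and Accrual) bear on success for CR at PET#2.

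- **The sized test.** The Study Summary gives its terms: "In order to have 84% power to detect an increase from the historical control of 20% rates of CR", and "at a one-tailed alpha of 10%, approximately 26 evaluable patients will be required total". Section 10.2 repeats 20%, 40%, 84% and 10%, and adds: "The target sample size for the primary response analysis is 26 patients, with 4 additional patients to be accrued to account for dropout". Neither place prints a critical number of responses.
- **The 40% sentence.** Section 10.2 and the Study Summary both say the treatment paradigm will merit further evaluation if 40% or more of patients achieve CR. This is the only one of the three worded as a decision.
- **The Bayesian option.** Section 10.2 says "a single arm single stage Bayesian design with 26 patients may also be used", tabulates posterior probabilities for 11 to 15 responses, and concludes: "to be more than 80% sure that the response rate exceeds 40%, at least 13 of 26 responses would need to be observed".

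No sentence ranks the three or says when the Bayesian design applies. Section 10.3.1 names none of them for the final analysis. It gives a proportion with an exact 95% confidence interval and observes whether 50% lies inside. For monitoring it says: "Futility will be indicated if at most 1/10, 3/15 or 5/20 evaluable patients have a response".

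**The concern.** The three statements look like one criterion in different words, but they translate into different counts out of 26. If they disagree over likely results, two statisticians following the same plan could report opposite conclusions. The power a reader takes from the protocol would then describe at most one of the rules. With a single arm and 26 patients, the count is the whole of the primary evidence, so its cut-off should be fixed in advance.

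**Working it through.** **Inputs.** Null rate 20%, target rate 40%, one-sided alpha 10%, stated power 84%, N = 26 (Study Summary and section 10.2). Bayesian threshold 13/26 and posterior table (section 10.2). Futility limits 1/10, 3/15 and 5/20 (section 10.3.1). The prior is described only as non-informative; I assume uniform, Beta(1,1).

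**1. The stated 84%.** Normal approximation:

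- critical rate = 0.20 + 1.2816 × √(0.20 × 0.80 / 26) = 0.3005, or 0.3005 × 26 = 7.8 responses
- power = Φ[(0.40 − 0.3005) / √(0.40 × 0.60 / 26)] = Φ(1.035) = 85.0%

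The arcsine version gives 83.5%. So 84% is an approximation-based figure for the one-sided test.

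**2. The exact test.** With X ~ Bin(26, p):

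- at least 8/26: P(X ≥ 8 | 0.20) = 13.1%, above 10%; power at 40% is 87.8%
- at least 9/26: P(X ≥ 9 | 0.20) = 5.9%; power at 40% is 77.4%

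The exact 10% test therefore needs 9/26. No cut-off gives 84%.

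**3. The 40% sentence.** Read as an observed rate, 0.40 × 26 = 10.4, so at least 11/26.

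**4. The Bayesian threshold.** The posterior is Beta(1 + x, 27 − x). P(rate > 40%) for x = 11 to 15 is 0.613, 0.750, 0.855, 0.926 and 0.966. This matches the printed table within 0.01 and confirms 13 as the first count above 0.80.

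**5. Chance of a positive verdict, by rule (no futility stops).**

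| Rule | Count needed | True 20% | True 40% | True 50% |
|---|---|---|---|---|
| Exact test against 20% | 9 or more | 5.9% | 77.4% | 96.2% |
| Observed rate at least 40% | 11 or more | 0.8% | 47.9% | 83.7% |
| Bayesian, 80% sure above 40% | 13 or more | 0.06% | 19.9% | 57.7% |

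**6. Where they disagree.** Results of 9 or 10 pass only the test. Results of 11 or 12 pass the test and the 40% sentence but not the Bayesian threshold.

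- P(9 to 12) = 57.5% at a true 40%, 38.5% at 50%, 34.7% at 30% and 5.9% at 20%
- P(11 or 12) = 27.9% at a true 40%
- with the printed futility limits applied at 10, 15 and 20 patients only, P(9 to 12) at 40% falls to 54.2%

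**7. Does section 10.3.1 settle it?** No. The exact 95% interval contains 50% for every count from 8 to 18, so that check treats 9 to 12 no differently from 13.

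**8. Fit with futility.** At 6/20 the most that can be reached is 6 + 6 = 12, so 13/26 is out of reach, yet the printed limit stops only at 5/20 or fewer. Under the same three looks, reaching 20 patients with exactly 6 responses has probability 10.4% at a true 40% and 16.0% at 30%.

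**The case against.** The best defence is that only the 40% sentence is worded as a decision. On that view the sized test merely justifies N, and the Bayesian sentence interprets a table: it says what 80% certainty would take, and no text makes that certainty a condition of success. The Study Summary omits the Bayesian design altogether. Much of this stands. The protocol never calls 13/26 a go rule, and 9/26 is derived rather than printed (the normal approximation would give 8, widening the zone to 8 to 12). But the defence has to be supplied by the reader. If the 40% sentence governs as an observed rate, power at the target is 47.9%, which does not fit the sample-size statement beside it. Results of 11 or 12 would still fall short of a count the section says would need to be seen.

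Two stronger readings are tempting and not supported.

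- A reader might infer that picking the rule after seeing the data inflates the false-positive rate. It does not: every result of 13 or more is also 11 or more and 9 or more, so the most lenient choice is the exact test itself, at 5.9%. Nor does anything suggest that such a choice is intended.
- A reader might take the 6/20 mismatch as proof that the futility limits are wrong. It shows only that they were not built around 13/26. Section 10.3.1 defines futility by the posterior for a rate above 50%, which is 0.039 at 6/20 under a uniform prior. By that definition 6/20 should stop too, a separate inconsistency.

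**Conclusion.** The concern holds as an ambiguity in the primary decision rule. Section 10.2 supports cut-offs of 9, 11 and 13 of 26 without ranking them, and at the design alternative the count more likely than not falls where they disagree (57.5%, or 54.2% with the printed stops). That majority is specific to rates near 40%; at the 50% the sponsor predicts it is 38.5%. What is left open is the chance of a positive verdict at a true 40%, anywhere from 20% to 77%. The stated 84% matches none of the three rules exactly.

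This rests on the exact binomial test for the 9/26 cut-off, an observed-rate reading of the 40% sentence, a uniform prior and 26 evaluable patients. The 5.9% ceiling on false positives holds for the exact test; a cut-off of 8 from the normal approximation would have a false-positive rate of 13.1%.

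**What to change.** Name one governing rule in section 10.2, with its critical count, and repeat it in the Study Summary and section 10.3.1. The simplest version:

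- make the exact one-sided test against 20% the decision, met at 9 or more of 26
- restate its power at 40% as about 77% at an actual alpha of 5.9%, in place of 84%
- reword the 40% sentence so that 40% is the target rate, not a threshold for the observed rate
- label the posterior table and the 13/26 sentence as supportive description with no bearing on success

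If the sponsor prefers 11/26 or 13/26, make it the only rule and state its own figures: 47.9% success at a true 40% and 0.8% at 20% for 11/26, or 19.9% and 0.06% for 13/26. With 13/26, also align the futility limits, since 6/20 already rules it out.

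The change is wording only, with no new data or patients. The small downside is a less favourable stated power.

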10.3 Data Analyses Plans

10.3.1 Analytic Plan for Primary Objective

To assess the primary objective of response rate following PET (2) performed after 3 doses of pembrolizumab, we will assess PET response using the 5 point Deauville criteria. Patients with a Deauville score of 1-3 will be considered a complete response. Patients will be evaluable for response assessment if they have received at least one dose of pembrolizumab. Response will be determined in all patients after induction (PET # 2) and after chemotherapy (PET # 3) using a proportion and an exact binomial 95% confidence interval. It will be observed whether 50% is in the confidence interval. Continuous futility monitoring will occur using the method of Lee & Liu. ⁵⁰ While this method may be used to identify a futile level of response after each patient, it will begin monitoring after 10 patients. Futility will be indicated if at most 1/10, 3/15 or 5/20 evaluable patients have a response, assuming 26 total evaluable patients will be observed. For these calculations, futility means that the posterior probability that the response rate exceeds 50% is less than 10%.

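### The trial is sized to reject a 20% CR rate, but the primary analysis names no test of 20% and only notes whether 50% lies in a 95% interval, without ranking this against the plan's other benchmarks

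*Combined protocol and SAP*

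**What the plan says.** **Sizing.** The Study Summary (Statistical Methodology) reads: "In order to have 84% power to detect an increase from the historical control of 20% rates of CR", with a one-tailed alpha of 10%. Section 10.2 repeats the hypothesis, "from the baseline level of 20% in relapsed/refractory patients, to 40% with a power of 84% at an alpha level of 10" per cent, and the size: "The target sample size for the primary response analysis is 26 patients, with 4 additional patients to be accrued to account for dropout".

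**Go criterion.** The same two places say that the approach merits further study if 40% or more of patients reach CR at PET#2.

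**Optional Bayesian analysis.** Section 10.2 allows a single-stage Bayesian analysis and derives from its table that 13 of 26 responses are needed to be over 80% sure that the rate exceeds 40%.

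**Primary analysis.** Section 10.3.1 estimates response "using a proportion and an exact binomial 95% confidence interval" and continues: "It will be observed whether 50% is in the confidence interval". It then gives futility bounds of 1/10, 3/15 and 5/20. The 50% is the CR rate predicted in section 2.1.

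Neither 10.3.1 nor any other section gives a test, p-value or critical value for the 20% rate.

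**The concern.** A plan that states a null rate, an alternative, an alpha and a power has promised a test. The section that should carry it out does something else: it compares a two-sided 95% interval with the rate the investigators hope for.

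Failing to exclude 50% is not evidence for 50%, least of all with 26 patients. Nor is the observation ordered by benefit: a result compatible with 20% can satisfy it, and a very good result does not.

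The other benchmarks do not fill the gap, because they have different operating characteristics and the plan does not say which one governs. For some results the conclusion could then depend on a benchmark chosen after the data are seen.

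**Working it through.** **Inputs.** Null 20%, alternative 40%, one-sided alpha 10%, power 84%, n = 26 (Study Summary; 10.2). Exact 95% interval and 50% benchmark (10.3.1). The 40% criterion is read as an observed proportion: 0.40 × 26 = 10.4, so at least 11/26. Posterior threshold: at least 13/26 (10.2).

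**1. The stated power.** By the normal approximation, power = Φ[(0.20√26 − 1.2816√(0.2 × 0.8)) / √(0.4 × 0.6)] = Φ[(1.0198 − 0.5126) / 0.4899] = Φ(1.035) = 0.850. The arcsine version gives 0.835. So 84% is an approximate figure for a one-sided test of 20% against 40%.

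**2. The exact version of that test.** For X ~ Bin(26, 0.2), P(X ≥ 8) = 13.1%, above 10%, and P(X ≥ 9) = 5.9%. The cut-off is therefore 9/26, with power P(X ≥ 9 | 0.4) = 77.4%.

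**3. The 50% observation.** Clopper-Pearson 95% limits for x of 26:

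| x | 95% interval | 20% inside | 50% inside |
|---|---|---|---|
| 7 | 11.6–47.8% | yes | no |
| 8 | 14.3–51.8% | yes | yes |
| 9 | 17.2–55.7% | yes | yes |
| 10 | 20.2–59.4% | no | yes |
| 18 | 48.2–85.7% | no | yes |
| 19 | 52.2–88.4% | no | no (above) |

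50% is inside for exactly 8 to 18 responses.

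**4. The benchmarks side by side** (exact binomial, futility stops ignored):

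| Benchmark | Region of 26 | Probability at 20% | At 40% | At 50% |
|---|---|---|---|---|
| 50% inside the interval | 8–18 | 13.1% | 87.8% | 97.1% |
| Exact test of 20% (not in the plan) | ≥ 9 | 5.9% | 77.4% | 96.2% |
| Observed CR of 40% or more | ≥ 11 | 0.8% | 47.9% | 83.7% |
| Posterior threshold (optional) | ≥ 13 | 0.06% | 19.9% | 57.7% |

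A uniform prior gives posterior probabilities of a rate above 40% of 0.61, 0.75, 0.86, 0.93 and 0.97 for 11 to 15 responses. These agree with the plan's table to within 0.01.

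**5. Where the benchmarks part.**
- 8/26: 50% is inside the interval, but 20% is not rejected and the 40% criterion is missed.
- 9 or 10/26: 20% would be rejected and 50% is inside, but the 40% criterion is missed.
- 11 or 12/26: the 40% criterion is met, the posterior threshold is not.
- 19/26 or more: every other benchmark is met, but 50% lies outside, below the interval.

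**The case against.** A reader might infer that any result from 8 to 18 of 26 counts as a pass, or that 13.1% is the trial's false-positive rate. The documents support neither. The wording on 50% is descriptive and nothing makes it a success rule. The plan has a go criterion, stated twice, and 8/26 (30.8%) fails both that and the posterior threshold. The 13.1% is the chance of an observation, not a type I error, and it falls to 10.1% once the futility bounds in 10.3.1 are applied.

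The go criterion is also stricter than the missing test. At 11/26 the exact 95% interval is 23.4–63.1%, and the chance of 11 or more at a true 20% is 0.8%. A trial that meets it has excluded 20%. Finally, section 10.0 describes the aim as estimation, a 95% interval beside a one-sided 10% sizing alpha is not an error in itself, and readers can compare the reported interval with 20% themselves.

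All this stands against the stronger reading. It does not supply the missing test:
- The go criterion protects against a false claim but has 47.9% power at the 40% for which 84% is stated. It reaches 83.7% only at a true 50%, which is not the alternative in the sizing text.
- Reading the 95% interval against 20% amounts to a one-sided 2.5% test. It needs at least 10/26 and has 63.6% power at 40%.
- An estimation aim does not explain a stated null, alpha and power.

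**Conclusion.** The concern holds in this form: the hypothesis that justifies 26 patients has no specified test, the 50% observation cannot stand in for one, and the plan does not rank its benchmarks. Neither written threshold delivers the stated power at 40%: the exact figures are 47.9% for at least 11/26 and 19.9% for at least 13/26, and 77.4% for the exact test that matches the sizing hypothesis. The practical effect is largest at 8 to 12 and at 19 or more responses, where the benchmarks disagree.

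This rests on 26 evaluable patients, on reading the 40% criterion as an observed proportion, and on ignoring futility stops, which can only lower these powers. It is not a finding that the trial would declare success on weak data.

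**What to change.** **In 10.3.1**, replace the sentence on 50% with text such as:

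> *The null hypothesis that the CR rate is 20% or less will be tested by an exact one-sided binomial test at the 10% level (reject with at least 9 responses if 26 to 28 patients are evaluable, at least 10 if 29 or 30), reported with the one-sided 90% lower confidence limit. The exact 95% interval is descriptive.*

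The attained sizes for n = 26 to 30 are 5.9%, 7.4%, 9.0%, 4.9% and 6.1%.

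**In 10.2**, say which criterion decides the primary conclusion and how the others relate to it. One option: the test decides whether activity exceeds 20%, and the 40% already stated is the further threshold for going on. Give the 13/26 threshold a defined role, or label it supportive. Without this step the test would add one more unreconciled threshold.

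**In the Study Summary and 10.2**, restate the power for the rule used: exact power 77.4%, size 5.9%, at 9/26 or more.

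The cost is wording and a less favourable stated power. No extra patients or data are needed, and the change should be made before the primary endpoint is analysed.
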